study. Participants with a baseline GFR of < 30 will also have their potassium level measured at the one-month follow-up visit. Study medications will be appropriately adjusted depending on potassium level. Participants who have a potassium level of 5.0 or greater at any time in the study will receive a handout on how to avoid potassium-rich foods. Participants will return for blood pressure, potassium, and eGFR measurements following increases in dose. If a participant returns two weeks after a dose increase for a blood pressure and potassium measurement, and these blood pressure and potassium measurements are also within 30 days of an upcoming scheduled 2- or 5-month follow-up visit, the 2- or 5-month visit is not also required. In addition, participants will be provided with a list of side effects of telmisartan and will be provided with [name] home and cellular telephone numbers, in case the participant develops side effects or has questions. It is important to point out that in prior randomized trials of telmisartan therapy for prevention of cardiovascular events, telmisartan was well tolerated (19,66-68). For example, in the pilot trial of telmisartan in 36 PAD participants, there were no adverse events (19).

Minimizing risks related to muscle biopsy. The muscle biopsy procedure will be performed by [name] who has more than 30 years of experience performing these muscle biopsies, primarily as part of his clinical practice as a Board-Certified Neurologist. As in our muscle biopsy pilot study, completed in preparation for this proposal, the muscle biopsy procedures will be performed under sterile conditions using sterile technique. Local anesthesia will be obtained using subcutaneous lidocaine. All participants will be provided with written and verbal instructions about wound care and will be advised to contact [name] immediately if any signs of wound infection occur.

Many PAD participants take anti-platelet therapy to prevent cardiac and cerebrovascular events. If potential participants are taking anti-platelet therapy, they may be asked to hold their anti-platelet therapy during the seven days leading up to each muscle biopsy procedure. Participants who undergo bilateral biopsies may be asked to hold their anti-platelet therapy for approximately 14 days. At follow-up, if the participant has had a coronary revascularization with stenting in the previous three months, the participant will not be asked to hold their anti-platelet therapy. Permission from the participant's physician will be obtained before asking the participant to hold their anti-platelet therapy. If the participant's physician does not provide permission for the patient to stop the anti-platelet therapy, then the participant will either be excluded from the muscle biopsy portion of the study or the biopsy will be performed while the participant is taking anti-platelet therapy. Participants who are taking warfarin or other anti-coagulant therapy will be excluded from the muscle biopsy portion of the study.

PROTOCOL TITLE: Telmisartan Plus Exercise to Improve Functioning in PAD: The TELEX Trial

Minimizing risk related to baseline and follow-up testing. All study coordinators undergo baseline training and are certified by [name] before beginning data collection. Training and certification involves ensuring that coordinators are trained in methods to help minimize falls. [name] or a senior study coordinator re-certifies coordinators approximately every six months to ensure continued adherence to study protocol. Those who are not adhering to protocol undergo additional training followed by re-certification.

Minimizing risk related to loss of confidentiality. The following methods will be employed to maintain confidentiality of participants. First, study recruitment letters will be mailed, using IRB-approved methods, only after notifying the participant's physician. The personal physician of each study participant will have the option of not allowing investigators to contact the potential participant. Lists of potentially eligible participants will be obtained by individuals who normally have access to these lists as part of their daily work requirements. Recruitment letters for potential participants identified from hospital and outpatient lists are prepared by research staff members whose job is to assist study investigators with recruitment. These research staff members have completed training in the ethical conduct of human subject research, including maintaining participant confidentiality. Recruitment letters to potential participants identified from medical center lists are mailed in sealed envelopes and addressed to the potential participant. All potential participants who receive mailed information about the study will have the opportunity to call a voicemail system to ask NOT to be further contacted about this study. Secondly, only study investigators and key research staff will have access to the study database. Third, participants will be assigned a unique study identifier. Individual names will ultimately be removed from the study database and only the unique study identifier will be used to distinguish participants in the database. Fourth, collected data will be maintained in locked computer files and file cabinets to which only study investigators have access. Collected data will be used only for research purposes. Any published data will not contain individual identifiers.

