The TELEX Trial builds on our prior work. Prior study has established that patients with PAD have significant functional impairment and faster functional decline and mobility loss than people without PAD (1-6). We have successfully completed large randomized trials of exercise in PAD patients (43,60). Our preliminary evidence supports our hypotheses and shows that PAD participants taking an ACE inhibitor or an ARB have more favorable mitochondrial function and respond more favorably to an exercise intervention than those not taking these medications.

PROTOCOL TITLE: Telmisartan Plus Exercise to Improve Functioning in PAD: The TELEX Trial

2.3 *Scientific background and significance of research based on existing literature.*

A. Telmisartan improves oxygen consumption and running endurance in mice by up-regulating peroxisome proliferator activated receptor delta (PPAR δ) and increasing skeletal muscle levels of adenosine monophosphate-activated protein kinase (AMPK) (16,18). In cell culture and animal studies, telmisartan up-regulates PPAR δ and AMPK, suggesting a mechanism underlying beneficial effects of telmisartan on muscle contractile properties and energy production (16,18,36,37). PPAR δ , expressed in high concentrations in skeletal muscle, regulates the metabolic and contractile properties of myofibers (36,37). Mice that overexpress PPAR δ have greater oxidative Type I muscle fibers, improved oxygen consumption, enhanced whole-body insulin sensitivity, and greater walking endurance (36,37). Type I muscle fibers are rich in mitochondria that provide a steady supply of ATP and are fatigue resistant. AMPK is a major regulator of energy metabolism in skeletal muscle that directly up-regulates PGC-1 α , increases mitochondrial biogenesis, and enhances mitochondrial function (37).

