3.0 Inclusion and Exclusion Criteria

3.1 Screening for eligibility

Initial eligibility criteria will be assessed by telephone. Potential participants who remain eligible after the telephone screening will be scheduled for a baseline visit, where they will undergo additional testing to determine their eligibility for randomization.

3.2 Inclusion and Exclusion Criteria.

Inclusion Criteria. All participants will have PAD. PAD will be defined as follows. First, an ABI ≤ 0.90 at the baseline study visit is an inclusion criterion for PAD. ABI ≤ 0.90 is a well-accepted standard for defining PAD (61-64). Second, potential participants who have an ABI > 0.90 but ≤ 1.00 and experience a 20% or higher drop in ABI after heel-rise exercise will be eligible. Third, potential participants with an ABI > 0.90 who have vascular lab evidence of PAD or angiographic evidence of PAD will be eligible. Finally, potential participants with a history of lower extremity revascularization who do not meet the criterion above and have an ABI > 0.90 with a 20% or higher drop in ABI after heel-rise exercise will be eligible.

Exclusion Criteria.

1. Above or below knee amputation, critical limb ischemia, wheelchair confinement, inability to walk without a walker, or current foot ulcer. These are exclusion criteria because they prevent full participation in the intervention or imply an underlying impairment that is too severe to be improved with trial interventions.
2. Walking is limited by a condition other than PAD. This is an exclusion because the intervention is designed to improve PAD-related walking impairment.
3. > Class II NYHA heart failure or angina, increase in angina, angina at rest, or abnormal baseline treadmill stress test. This is an

PROTOCOL TITLE: Telmisartan Plus Exercise to Improve Functioning in PAD: The TELEX Trial

exclusion because exercise may not be safe for these individuals. Potential participants may become eligible following an abnormal baseline treadmill stress test if they have evidence of an absence of coronary ischemia based on testing with their own physician.

4. Currently taking an angiotensin receptor blocker or an ACE inhibitor or use of these medications in the past three months. This is an exclusion because these individuals are already receiving a major component of the trial intervention.

5. Currently taking aliskiren (Tekturna). This is an exclusion because telmisartan may not be safe to take concurrently with aliskiren.

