Other measures related to skeletal muscle quality and function and related to fat measures of inflammation and senescence may also be performed at Northwestern, the University of Florida, and/or the University of Kentucky, Mayo Clinic or at other institutions as designated by the Principal Investigator.

PROTOCOL TITLE: Telmisartan Plus Exercise to Improve Functioning in PAD: The TELEX Trial

Medications. Participants and their physicians will be asked not to change their medications during the study if possible. Participants will be asked to bring all of their medications to baseline and follow-up visits and to monthly blood pressure check visits. We will systematically record names and doses of medications and inquire about medication changes at each of these visits. If we find differences in the use of specific medications between study groups (such as statins or cilostazol), we will adjust for these differences.

Other measures. Body mass index (BMI) will be assessed at baseline and follow-up by objectively measuring height and weight. Patient report will be used to document comorbidities. A four-meter walk test will be administered at usual and fastest pace at the baseline and follow-up visits. Participants will be asked to perform the usual paced four-meter walk at usual pace and the “fast paced” four meter walk at their fastest pace. Each of these short walks will be performed twice. Participants will be asked to complete a series of standing balance exercises and chair stands. Participants will undergo a physical exam by a physician and will have the blood pressure in their arm checked. Participants may be asked to return for a second blood pressure measurement at the discretion of the investigator (e.g. if the sitting blood pressure is not consistent with their typical blood pressure or if changes in medical condition or treatment may have spuriously altered the blood pressure value).

9.3 Overview of protection against risks.

Adequacy of protection against risks and methods to minimize potential risks. [name] and the study safety officers are responsible for overseeing results of monthly blood pressure checks and regularly scheduled potassium levels and measures of renal function and will follow up with the participant and/or their physician as necessary.

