Statistical Analyses. Analyses will be performed according to the intention to treat principle. Data will be analyzed according to each participant's originally assigned group, irrespective of whether the participant adheres to the assigned group. For the Primary Aim, we will use analysis of covariance (ANCOVA) to compare changes in six-minute walk performance at 6-month follow-up between Group A+B combined and Group C+D combined, adjusting for study site (Northwestern or Tulane) and randomization to exercise status. For our Secondary Aim 1 and our Secondary Aim 2, we will use two sample two-tailed t-tests to compare changes in six-minute walk at 6-month follow-up between Groups A and B, between Groups A and C, and between Groups B and D, all stratified by study site. For our Secondary Aim 3, we will use ANCOVA to compare changes in maximal treadmill walking distance, the WIQ, and the SF-36 physical functioning score between Groups A + B vs. Groups C + D, adjusting for study site and randomization to exercise. For our Tertiary Specific Aim 1, we will use t-tests to compare maximal treadmill walking distance, the WIQ, and the SF-36 functioning score, between Groups B and D stratified by study site. For our Tertiary Specific Aim 2, we will use t-tests to compare maximal treadmill walking distance, the WIQ, and the SF-36 physical functioning score, between Groups A and B, and between Groups A and C, respectively, also stratified by study site. For our Exploratory Aims, we will use ANCOVA to compare changes in gastrocnemius muscle biopsy measures of each muscle measure between Groups A+B vs. C+D adjusting for study site and randomization to exercise. We will also compare Groups A, B, and C, respectively vs. Group D using two sample t-test stratified by study site. When the distribution of changes in the primary, secondary, and exploratory outcomes of interest is "very non-Gaussian", we will either apply appropriate transformation before conducting t-tests or perform Wilcoxon rank-sum test for the comparisons. Prior to analyses, we will also check the potential imbalance of socio-demographic factors and prognostic factors (such as age, sex, race, baseline outcome measure, ABI, BMI, smoking status, comorbidities, and relevant medication use) between the two groups using t-tests for continuous factors and chi-square test for discrete factors. If there is any indication of major imbalance in these factors or baseline variables are associated with the change in outcome of interest, we will perform ANCOVA to further adjust for the relevant baseline factors as potential confounders, in addition to randomization to exercise status and site, for two-group comparison. Similar analysis will be performed for exploratory aims. In the analysis for the secondary, tertiary and exploratory aims, we will not adjust for multiple testing. However, we will report all the results regardless of their significance to present an overall picture of the treatment effect of

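### The medication-adjustment rule in section 9.2 is not limited to baseline use, so as written it allows covariate adjustment for drugs started after randomisation

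*Combined protocol and SAP*

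**What the plan says.** Section 3.2 bars ACE inhibitors and ARBs, current or within three months (criterion 4): "This is an exclusion because these individuals are already receiving a major component of the trial intervention". It bars aliskiren (criterion 5): "This is an exclusion because telmisartan may not be safe to take concurrently with aliskiren".

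After entry, the Medications paragraph of section 9.2 does three things in turn:

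- It makes a general request: "Participants and their physicians will be asked not to change their medications during the study if possible".
- It sets up recording at the baseline, follow-up and monthly blood-pressure visits: "We will systematically record names and doses of medications and inquire about medication changes at each of these visits".
- It gives an analysis rule: "If we find differences in the use of specific medications between study groups (such as statins or cilostazol), we will adjust for these differences".

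The Statistical Analyses text in section 11.2 specifies intention to treat, with a primary ANCOVA adjusting for site and exercise assignment. On further covariates it says "Prior to analyses, we will also check the potential imbalance of socio-demographic factors and prognostic factors", and relevant medication use is on the list that follows. If there is major imbalance, or if baseline variables are associated with the change in outcome, "we will perform ANCOVA to further adjust for the relevant baseline factors as potential confounders".

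**The concern.** The section 9.2 rule is a positive commitment to adjust. It comes straight after a sentence about capturing medication changes during the trial and does not say which use counts: baseline, in-trial, or both. Section 11.2 points to baseline, but neither section refers to the other. An analyst could cite either one when choosing covariates for the primary comparison.

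The distinction matters because a drug started after randomisation can be a consequence of assignment. Telmisartan lowers blood pressure. A placebo participant whose pressure stays high is a natural candidate for an ACE inhibitor or ARB, and the prescriber need not be unblinded for this to happen. Section 2.2 also reports that "PAD participants taking an ACE inhibitor or an ARB have more favorable mitochondrial function and respond more favorably to an exercise intervention", so these drugs are not assumed neutral for walking outcomes.

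Conditioning on such a start compares all or nearly all of the telmisartan arm with a selected part of the placebo arm. Intention to treat does not prevent this. It fixes the group in which each participant is counted, not which covariates enter the model.

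**Working it through.** **The plan's own figure.** Section 11.2 gives 50 completers per pooled group, 0.566 SD, two-sided alpha 0.05 and 80% power. The noncentral t calculation gives 80.0%, so the figure reproduces.

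**Assumed inputs (none is in the documents).** The start rate on placebo is c_P = 5%, 10% or 20%. The start rate on telmisartan is c_T = 0 or 5%. The people who would start the drug on placebo make up the same share c_P of both arms, and their walk change is worse by g SD (better if g is negative). The started drug has no effect of its own. The model is change on arm, exercise assignment and an indicator for starting.

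**Shift in the adjusted estimate.** Randomisation makes the two arm means equal when telmisartan has no effect, so any non-zero arm coefficient is bias.

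- *Starts on placebo only.* The indicator removes the placebo starters. What remains is all of telmisartan (mean −c_P·g) against placebo non-starters (mean 0), so the bias is −c_P·g. For g = 0.5 this is −0.025, −0.05 and −0.10 SD.
- *Starts on both arms.* The pooled coefficient for starting is b = −g(1−c_P)(c_P+c_T) / [c_P(1−c_P) + c_T(1−c_T)], and the bias is b(c_P−c_T).
  - c_P = 0.20, c_T = 0.05, g = 0.5: b = −0.5 × 0.200/0.2075 = −0.482, so the bias is −0.482 × 0.15 = −0.072 SD.
  - c_P = 0.10, c_T = 0.05, g = 0.5: b = −0.5 × 0.135/0.1375 = −0.491, so the bias is −0.025 SD.
  - c_P = 0.10, c_T = 0.05, g = 0.25: the bias is −0.012 SD.

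**Rejection rates with no drug effect** (simulation, 50 per arm; nominal 2.5% on each side):

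| Starts, placebo / telmisartan | g | Bias (SD) | Favours telmisartan | Favours placebo |
|---|---|---|---|---|
| 5% / 0 | 0.5 | −0.025 | 2.0% | 3.3% |
| 10% / 0 | 0.5 | −0.05 | 1.5% | 4.1% |
| 20% / 0 | 0.5 | −0.10 | 0.8% | 6.9% |
| 20% / 0 | 0.25 | −0.05 | 1.4% | 4.1% |
| 20% / 5% | 0.5 | −0.07 | 1.2% | 5.3% |
| 10% / 5% | 0.5 | −0.025 | about 2% | about 3% |
| 10% / 5% | 0.25 | −0.012 | about 2% | about 2.5% |
| 20% / 0 | −0.5 | +0.10 | 6.8% | 0.8% |

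Without the start covariate, the bias is within 0.005 SD and each side rejects 2.2% to 2.7%.

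**Power with a true 0.566 SD effect** (g = 0.5, starts on placebo only). Adjusted power is 75%, 69% and 58% at 5%, 10% and 20%. Unadjusted power is 80%, 79% and 78%. Part of the adjusted loss is bias and part is lost precision. At 20%, the comparison is (0.566 − 0.10)/√(1/50 + 1/40) = 0.466/0.212 = 2.20, against a critical value of about 1.98.

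**In metres.** Section 11.2 equates about 40 m with 0.70 and 0.78 SD in two earlier trials. One SD is therefore about 40/0.78 = 51 m to 40/0.70 = 57 m, and 0.10 SD is about 5 to 6 m.

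**The case against.** **The analysis is governed by section 11.2.** Section 9.2 is a data-collection section, and its examples are statins and cilostazol. Section 11.2 fixes the primary ANCOVA, lists medication use among the factors to check and calls the added covariates baseline factors. On this view only a cross-reference is missing. Much of this stands: section 11.2 is good evidence that baseline use was meant. It does not withdraw the section 9.2 commitment, however, and the two texts allow different covariate sets.

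**The larger shifts need strong assumptions.** This also stands. They require no starts on telmisartan and a 0.5 SD prognostic gap. With starts at 10% and 5%, the shift is only 0.01 to 0.02 SD, and no document supports any particular rate, split or gap.

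**Stronger readings that the documents do not support:**

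- *That the plan clearly intends to adjust for in-trial drugs.* It does not say so; the wording only permits it.
- *That in-trial starts on placebo threaten the trial's power, and that this is a reason for the change.* If 5% to 20% of placebo participants gained half or all of the telmisartan effect, power would fall from 80% to between 78% and 61%. But intention to treat is meant to carry such starts, and nothing shows that new wording would prevent them. Section 2.3 also presents telmisartan as having muscle effects that other agents lack, so the full-effect cases are ceilings. These figures should not be used to support the fix.
- *That an aliskiren start would go unmanaged.* Medications are reviewed monthly (9.2), and safety officers follow up blood pressure, potassium and renal results (9.3). The dose can be reduced, or replaced with placebo, under blind (9.1), and telmisartan can be stopped at investigator discretion (14.0). No response is tied to the start itself, but one is possible. The manuals, DSMB charter and physician letter are not supplied and may name these drugs.

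**Conclusion.** The point holds as a wording conflict with a real analytic consequence. Section 9.2, followed literally, permits adjustment for post-randomisation drug use; section 11.2 suggests that only baseline use was intended. If in-trial starts were used as a covariate, the estimate would move by about 0.01 to 0.10 SD under the assumed start rates. It would move against telmisartan if starters do worse and in its favour if they do better, so neither a false harm nor a false benefit can be ruled out in advance. The size rests wholly on assumed start rates, arm split and prognostic gap. The case for settling it does not, because a covariate that assignment can influence does not belong in the primary comparison at any start rate. The aliskiren matter is a small gap in written policy.

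**What to change.** Before unblinding:

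1. In the Medications paragraph of section 9.2, limit adjustment to medication use at baseline and refer to section 11.2 for the method.
2. State in section 11.2 that the primary analysis is the intention-to-treat ANCOVA with no post-randomisation medication covariates.
3. Report in-trial starts of ACE inhibitors, non-study ARBs and aliskiren by arm.

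Items 1 and 2 are a clause each and cost nothing. Item 3 uses data that section 9.2 already collects.

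Optional and minor: have the existing monthly medication review flag any aliskiren start, with its date, to the safety officer, so that the blinded dose reduction or placebo replacement in section 9.1 can be used. The downside is a few extra flags to handle.
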